2.1. Clinical trial design

This will be a Four-Arm Parallel-Group Randomised Double Blinded Controlled Trial with a longitudinal design. Patients who fulfilled inclusion criteria will be randomly assigned to one of the four research groups (Group 1, 2, 3 or 4). Three groups will undergo an inpatient COMIRESTROKE (4 hours/day for 3 weeks). Group 1 (COMIRESTROKE – ICF) will undergo individualised rehabilitation therapy embodying the ICF system as a therapeutic tool, where current needs and wishes of the person after IS are integrated into an interdisciplinary team rehabilitation programme management. Group 2 and 3 will undergo a standard comprehensive intensive rehabilitation program three hours per day (39) plus one hour of specific PT (an individual neuroproprioceptive "facilitation inhibition" for Group 2, a technology-based training for Group 3). Group 4 will undergo standard care and will serve as comparative one to the intensified intervention groups.

Participants will be examined four times (Figure 1). At the beginning and after three weeks of hospitalization (both primary, secondary outcomes and a blood draw will be obtained for total RNA extraction, cDNA synthesis and real-time QPCR assessment of lncRNA candidates previously identified as potential therapeutic influencers in ischemic stroke), and then three months and one year after the end of the program (primary outcomes only).

Figure 1: Design of the study

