2.9. Measuring the effectiveness of rehabilitation

To test hypothesis I., i.e., a positive influence on all outcomes, the effect of therapy for each therapeutic group will be assessed separately by paired t-tests performed on pre-test and post-test scores. The Wilcoxon rank test will be used on data where normal distribution cannot be expected.

To test hypotheses II. and III, a comparison between therapeutic groups will be performed using two sample Student t-tests on differences between measurement time points (or Wilcoxon tests respectively for data, where normal distribution of the differences cannot be expected). For hypothesis II, the COMIRESTROKE - ICF group will be compared against the rest of the participants. For hypothesis III, the COMIRESTROKE - NEFI group will be compared against the rest of the participants. A one-sided alternative will be tested according to our hypotheses. We will also implement the one-way ANOVA test to jointly compare all three groups for prepost differences. In addition, a Tukey post-hoc comparison will be made to detect any further group differences beyond our hypotheses.

To assess the overall impact of rehabilitation and to compare effectiveness of different therapeutic approaches for Hypotheses I – III in more complex way, and to test for effect of other covariates in Hypothesis IV, a linear mixed effect model will be used with random patient effect fitted to longitudinal patient data. Measurement effect, group effect and their interaction, as well as effects of other covariates such as the level of disability in admission time will be tested by F test.

To address Goal I, correlations between changes in different examination scores will be evaluated using Pearson correlation coefficient and its nonparametric analogies. A cluster analysis will be performed to identify different phenotypes. This will allow the identification of different groups of patients in relation to the efficacy of the neuro-rehabilitation programs.

To address Goal II, for selected multi-item instruments, item-response theory (IRT) and generalized linear regression models will be used to study differential item functioning with respect to rehabilitation groups. Account will be taken for other respondent characteristics. Use will be made of differential item functioning in change (DIF-C) analysis (7) in order to detect between-group differences.

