2.10. Statistical software

Analysis will be performed using the free statistical environment R (98) and its libraries. The lme (99) and nlme (100) library will be used for implementing mixed effect models. Library difNLR (101) will be used for the detection of DIF. Modules of the interactive ShinyItemAnalysis application will enable lme (99), nlme (100) and difNLR (101) library sample analyses to be interactively displayed (102).

3. Discussion

Undoubtedly, early intensive and complex rehabilitation is necessary for people after ischemic stroke (103). To address all functions and activities of the patient, the ICF model (3) provides systematic categorization potentially increasing the effectiveness of therapy (104). This clinical trial will implement a biopsychosocial approach in which individual goals set by an interdisciplinary team and rehabilitator will take into account the functioning, activity and participation level of the patient. To date, no study implementing the ICF model, has evaluated the effectiveness of rehabilitation in comparison with other interventions. (14, 105).

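### Read plainly, the mixed model assumes equal variance and equal correlation across four unevenly spaced visits; an unstructured covariance should be specified for the four-visit primary outcomes

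*Combined protocol and SAP*

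**What the plan says.** The model is described in section 2.9 of the combined protocol and SAP: "a linear mixed effect model will be used with random patient effect fitted to longitudinal patient data". The terms tested by F test are "Measurement effect, group effect and their interaction", plus covariates such as disability at admission. Section 2.10 adds: "The lme (99) and nlme (100) library will be used for implementing mixed effect models"; reference 99 is the lme4 paper. Neither section names a random slope, a residual correlation structure, visit-specific variances or robust standard errors.

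The model is meant to "compare effectiveness of different therapeutic approaches for Hypotheses I – III in more complex way" and to test covariates for Hypothesis IV. Section 2.9 also plans simpler tests:
- Hypothesis I: paired t-tests within each therapeutic group.
- Hypotheses II and III: "two sample Student t-tests on differences between measurement time points", one arm against all other participants, for which "A one-sided alternative will be tested according to our hypotheses".
- A one-way ANOVA with Tukey comparisons of pre-post differences, described for three groups.

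On visits, section 2.1 has baseline, 3 weeks, "and then three months and one year after the end of the program (primary outcomes only"). Table 2 marks PROMIS and WHODAS 2.0 at all four visits. Its GAS row carries no marks, and section 2.5.1 rates the different goal types at different times. Secondary outcomes have at most two visits. Section 2.4 counts the follow-up months from admission, whereas section 2.1 counts them from the end of the program; the two need to be reconciled.

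**The concern.** A single random patient effect with independent residuals of constant variance gives every pair of visits the same correlation. Here the gaps between neighbouring visits run from 3 weeks to about 9 months, and section 3 describes the period as one of spontaneous improvement. Equal correlation over such gaps is a strong assumption, and the plan gives no reason for it.

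If it fails, one pooled residual variance serves every change contrast. It is too large where the true change variance is small (early) and too small where that variance is large (late).

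The model carries weight. Hypothesis I claims a larger effect than control, but the tests listed for it are within-arm, the ANOVA is described for three groups, and the tests for II and III pool all other participants. The mixed model is therefore the only analysis explicitly assigned to the between-group part of Hypothesis I. It is also the only one named for Hypothesis IV, and section 2.7 sends baseline imbalances to the longitudinal models.

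**Working it through.** The plan gives no figure on this point. Its one calculated number, 70 per group in section 2.6, comes from a two-group comparison and does not enter here.

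**Inputs.** From the documents: four visits, four arms at 1:1:1:1 and 210 patients, so 210/4 = 52.5 per arm (52 used below). Assumed, because the documents give no correlations or visit SDs: equal SD at every visit, complete data, and the correlations shown below.

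**Formulas.** For complete balanced data:
- fitted residual variance = mean variance − mean covariance;
- model variance of a change contrast is proportional to 2 × residual variance;
- true variance is proportional to v0 + vt − 2·cov(0,t), which with unit SD is 2(1 − ρ0t);
- SE ratio r = √[residual variance / (1 − ρ0t)];
- true size of a two-sided 5% test = 2·P(Z > 1.96r);
- power of a contrast designed for 80% = P(Z > 1.96r − 2.80).

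**One case in full.** Take baseline correlations .75/.55/.40 (3 weeks/3 months/12 months) and a mean of .65 for the three correlations among later visits. The mean of all six is (1.70 + 3 × .65)/6 = .608, so the residual variance is .392. At 12 months r = √(.392/.60) = 0.81, and the size is 2·P(Z > 1.58) = 11.3%.

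**Range.** The result needs all six correlations, so the later-visit mean is varied from .5 to .8:

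| Baseline correlations | Later-visit mean | Residual variance | SE ratio 3 wk / 3 mo / 12 mo | Two-sided size (%) | 3-week power (%) |
|---|---|---|---|---|---|
| .75/.55/.40 | .50 | .467 | 1.37 / 1.02 / 0.88 | 0.7 / 4.6 / 8.4 | 55 |
| .75/.55/.40 | .65 | .392 | 1.25 / 0.93 / 0.81 | 1.4 / 6.7 / 11.3 | 64 |
| .75/.55/.40 | .80 | .317 | 1.13 / 0.84 / 0.73 | 2.7 / 10.0 / 15.4 | 72 |
| .8/.7/.6 | .50 | .400 | 1.41 / 1.15 / 1.00 | 0.6 / 2.4 / 5.0 | 51 |
| .8/.7/.6 | .65 | .325 | 1.27 / 1.04 / 0.90 | 1.2 / 4.1 / 7.7 | 62 |
| .8/.7/.6 | .80 | .250 | 1.12 / 0.91 / 0.79 | 2.8 / 7.4 / 12.1 | 73 |

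The 3-week contrast is conservative in every row. The 12-month contrast is anti-conservative in every row but one, where it is exactly nominal. The 3-month contrast changes direction.

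**The planned F test.** The group-by-time F test was simulated 20,000 times per scenario with 52 patients in each of four arms and no true effect:
- autoregressive correlation by visit, adjacent value .5 to .9: 6.1% to 7.6%;
- decay by calendar time, .90 to .95 per month, visits at 0, 0.75, 3.75 and 12.75 months: 8.7% to 9.5%;
- the six rows of the table, later-visit correlations set equal: 5.5% to 8.3%.

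**Where nothing goes wrong.**
- Equal correlation and variance: ratio 1.00 for every contrast; F test 5.1%.
- Two visits: 2 × (mean variance − covariance) = v0 + v1 − 2·cov, the true variance, even with unequal variances. The contrast is the change-score t-test.
- Main effect of a patient-level covariate, complete data: it rests on the patient's mean over visits, whose variance is (mean variance + 3 × mean covariance)/4. The fitted model matches both quantities, so this test keeps its size. Covariate-by-visit terms do not have this protection.

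**The case against.** The strongest reply is that Hypotheses II and III are tested by t-tests on differences, which use the variance of the differences themselves. A reader might infer that the long-term ICF claim under Hypothesis II necessarily gets standard errors that are too small, and that the planned 3-week comparison loses power. The documents do not support that: these effects reach II and III only through the additional mixed-model analysis. This part of the reply stands in full.

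A reader might also infer that the plan forces equal correlation and certainly gives wrong standard errors. That too goes further than the text. The structure is inferred from silence, nlme can fit residual correlation and unequal variances, and the documents hold no correlation data. If correlations and variances are equal, the model is correct. What remains is that the plain reading is a random intercept. If another structure was intended, the plan should say so, because a covariance chosen after seeing the data adds analyst freedom. Either way the same edit is needed.

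Third, the plan names F tests, not visit-specific contrasts, so the 12-month figures describe tests that a reader would have to take from the model. That is fair. For the planned F test the inflation is smaller, which is why it is reported separately.

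Finally, the change-score t-tests drop patients who lack either visit. That is a separate missing-data question, and no part of this point rests on it.

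**Conclusion.** The point holds in a limited form. For PROMIS and WHODAS 2.0, the model as written assumes equal variance and correlation over four uneven visits. If correlation decays, the group-by-time F test runs at roughly 6-10%. A 12-month contrast from the model has a two-sided size of about 8-15% under the stronger decay and 5-12% under the milder one. The 3-week contrast is conservative. The 3-month direction depends on correlations among the later visits. All these sizes rest on assumed correlations, equal SDs and complete data.

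The between-group part of Hypothesis I and the mixed-model look at II and III are exposed. Hypothesis IV depends on the same model. With complete data the distortion there enters through covariate-by-visit terms, which is where a predictor of improvement would show, rather than through covariate main effects. Two-visit outcomes and the t-tests for II and III are not affected. GAS cannot be placed from Table 2.

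This should be changed because the better method is specific and cheap, not because an error of known size has been shown.

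**What to change.** For outcomes measured at all four visits, state in section 2.9 that the longitudinal model has visit as a categorical factor and an unstructured covariance, fitted by REML to all available visits (in nlme: gls with corSymm for the correlations and varIdent for visit-specific variances). Take the group-by-visit F test and the visit-specific arm contrasts from this model. Keep the t-tests as planned.

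Name a simpler structure in advance for use if the model does not converge, and state the denominator degrees of freedom. With the residual degrees of freedom that gls uses, the unstructured F test ran at 5.4-5.5% in the same simulations of the six tabled scenarios.

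The cost is ten covariance parameters (four variances, six correlations) instead of two, which is feasible with about 210 patients. Visits, data collection and sample size do not change, and the package is already named. For two-visit outcomes the complete-data change contrast stays the same.

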2.2. Eligibility criteria and subgroups

Participants will be identified by specialists in neurology and rehabilitation from inpatients at the Department of Acute Care, Department of Neurology, Thomayer University Hospital or University Hospital Kralovske Vinohrady, Prague, Czech Republic.

Inclusion criteria: Adults (18 - 85 years) after the first ischemic stroke in early sub-acute phase (40, 41), with a slight to moderately severe disability [2 - 4 on the Modified Rankin Scale (42)],

with minimal or moderate motor deficit of upper or lower extremities (on NIHSS Item 5 or 6 scores 1–3 points) who were able to perform activities of daily living prior to stroke event [0 – 2 on the Pre-Stroke Modified Rankin Score (43)], with a potential to accept 4 hours of comprehensive rehabilitation per day and to profit from the physiotherapy. Czech is their native language or its knowledge is at the level of the mother tongue.

Exclusion criteria: Low level of consciousness (vegetative state and/or minimally conscious state); severe cognitive decline that would interfere with administration of the tests, premorbid illiteracy, severe visual and/or auditory deficit that would prevent proper completion of the tests; behavioural disorders and/or lack of cooperation with therapist; and severe medical problems with a poor prognosis, (e.g., severe frailty, advanced and incurable cancer, fracture, cardiovascular disorders as chronic heart failure NYHA III, IV, symptomatic coronary artery disease Angina Severity Class III, IV, respiratory insufficiency as chronic obstructive pulmonary disease GOLD IV, and other severe disease) (44).

Randomisation

All patients meeting the above criteria will be invited to participate and asked to provide a written informed consent. They will be randomly assigned (1:1:1:1) as soon as possible, but always within 48 hours of admission, into one of the four interventions (represented by Group 1, 2, 3 or 4) using offsite-independent randomization protocols (www.randomization.com). Concealed allocation will be performed using sequentially numbered opaque sealed envelopes only accessible by research personnel with no involvement in the trial.

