2.6. Estimated size

It is estimated that approximately 110 people will be recruited to the clinical trial each year. This number is based on the fulfilment of performance and quality indicators report of cerebrovascular care at the Centre for Highly Specialized Patient Care for Stroke Patients at Thomayer Hospital 2019. A total of 210 people is expected to be enrolled in the clinical trial over a period of two years (Figure 2), corresponding to a required sample number of 70 patients per group. This value is necessary in order to detect a significant difference in improvement

between two groups when achieving a mean difference effect (Cohen's d = 0.5), a significance level of $\alpha = .05$ and a strength of $1-\beta = .80$. The sample size was determined based on the minimal clinically significant change on a Berg balance scale (96).

Figure 2: Planned recruitment and randomisation process

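### The mixed model for Hypotheses I to III is specified only through F tests: no treatment contrast is named, and Hypothesis I has no named comparison with Group 4

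*Combined protocol and SAP*

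**What the plan says.** Section 2.9 introduces the model with the aim "To assess the overall impact of rehabilitation and to compare effectiveness of different therapeutic approaches" for Hypotheses I to III, and to examine covariates for Hypothesis IV. The specification is that "a linear mixed effect model will be used with random patient effect fitted to longitudinal patient data", and that "Measurement effect, group effect and their interaction", along with covariate effects, "will be tested by F test". No contrast, visit or effect estimate is named for this model.

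Section 2.1 states "Participants will be examined four times": at baseline, after three weeks, and "then three months and one year after the end of the program (primary outcomes only"). Primary outcomes therefore have up to four visits and secondary outcomes have two. Section 2.2 has four arms, with patients "randomly assigned (1:1:1:1) as soon as possible". Section 2.7 says only that baseline differences, if observed, will be allowed for in the longitudinal models.

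Section 2.9 also lists other tests:
- **Hypothesis I:** paired pre-post t-tests within each group.
- **Hypotheses II and III:** one-sided two-sample t-tests on change, ICF against everyone else and NEFI against everyone else.
- **In addition:** a one-way ANOVA on change, described as covering three groups, with Tukey comparisons for differences outside the hypotheses.

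**The concern.** Hypotheses I to III in section 2.8 are directional and arm-specific. Hypothesis I says each programme beats the control group. Hypothesis II says ICF does best on the primary outcomes, including at three and twelve months. Hypothesis III says NEFI does best on the secondary outcomes. The model presented as the fuller test of these claims is judged by statistics that carry neither direction nor arm.

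The group F has a further problem. With baseline among the responses, its meaning depends on coding that the plan does not give. With sum-to-zero coding or sequential tests on balanced data, it compares arm means over all visits, one of them before treatment. With treatment coding and marginal tests, it compares the arms at baseline. Neither is a treatment effect.

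Hypothesis I is where this matters most. A within-group paired test cannot separate a programme's effect from spontaneous recovery, and the ANOVA as described covers three groups in a four-arm trial. The mixed model is the only analysis that plausibly brings in Group 4 for this hypothesis, and it names no comparison with it.

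**Working it through.** **Inputs from the documents.** Four arms at equal allocation; four visits for primary outcomes and two for secondary outcomes; α = 0.05; power 0.80; an effect on improvement described as "achieving a mean difference effect (Cohen's d = 0.5"); 70 per group; 210 in total.

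**Assumptions, not in the documents.** Baseline is a level of the measurement factor. Correlation ρ is equal between visits, with range 0.3 to 0.8. There is no dropout. The d applies to the SD of change. Tests are two-sided.

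**The plan's own figure.** n = 2(1.960 + 0.842)²/0.5² = 62.8, so 63 per group (64 by exact t); one-sided it is 50 (51). The stated 70 is not reproduced; 63/0.90 = 70 would match a 10% dropout allowance, but none is stated. With 70 per group, pairwise power is 0.84. Since 210/4 = 52.5, results are given for n = 70 and n = 52 per arm.

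**Set-up.** With unit variance at each visit, the SD of change is √(2(1 − ρ)), so the effect is δ = 0.5√(2(1 − ρ)) and δ²/(1 − ρ) = 0.5. T is the number of visits.
- A is the sum of squared arm deviations: 0.75 if one arm differs from the other three; 0.5 if two arms are δ apart and the others lie midway.
- V is the centred sum of squares of the visit pattern: 0.75 for (0,1,1,1) or (0,1,0,0); 0.5 for (0,1).
- m is the mean of that pattern: 0.75, 0.25 and 0.5 respectively.

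**Interaction F.** λ = nAVδ²/(1 − ρ) = 0.5nAV, so ρ cancels. The df are 3(T − 1) and (T − 1)(4n − 4): (4 − 1)(4 − 1) = 9 numerator df for four visits and 3 for two. Example: n = 52, one arm differing, four visits: λ = 0.5 × 52 × 0.75 × 0.75 = 14.6, and F(9, 612) has power 0.76. The same λ on 1 df, which is the matched contrast, has power 0.97.

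| Scenario | Interaction F, n = 70 / 52 | Matched 1-df contrast |
|---|---|---|
| 4 visits, one arm differs | 0.89 / 0.76 | 0.99 / 0.97 |
| 4 visits, two extreme arms | 0.70 / 0.54 | 0.95 / 0.88 |
| 2 visits, one arm differs | 0.87 / 0.74 | 0.95 / 0.87 |

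**Group F, averaged over visits.** λ = nAm²δ²/(ρ + (1 − ρ)/T), with 3 and 4n − 4 df. Example: n = 52, ρ = 0.5, sustained effect in one arm: λ = 52 × 0.75 × 0.5625 × 0.25/0.625 = 8.78, power 0.69.

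| One arm differs | ρ = 0.3, n = 70 / 52 | ρ = 0.5 | ρ = 0.8 |
|---|---|---|---|
| 4 visits, sustained | 0.98 / 0.93 | 0.83 / 0.69 | 0.31 / 0.24 |
| 4 visits, week 3 only | 0.22 / 0.17 | 0.14 / 0.11 | 0.07 / 0.07 |
| 2 visits | 0.59 / 0.45 | 0.38 / 0.29 | 0.15 / 0.12 |

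A simulation of 4,000 runs in two scenarios agreed with these formulas to within about one point.

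**The case against.** The strongest reply is that the mixed model is an additional analysis. Hypotheses II and III already have directed tests on change. The interaction F asks the right underlying question, whether change differs between arms, and failing to say which arm differs is true of any omnibus test and is ordinarily handled by follow-up comparisons. The plan also lists Tukey comparisons. Neither the factor coding nor the type of F test is stated, so the reading as a baseline difference is one possibility among several.

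Much of this stands. The interaction is a legitimate test, and the directed t-tests must be credited. Two things remain. Those t-tests pool Group 4 with the other programmes, so a positive result would not show that ICF or NEFI is the best programme. And the Tukey step is attached to a three-group ANOVA and reserved for differences outside the hypotheses, so it does not supply Hypothesis I's comparison with Group 4 as written.

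A reader might go further and infer that both F tests throw away most of the power, since a 1-df test with 80% power (λ = 7.85) has only 45% if the same λ is spread over 9 df. The documents do not support that. The interaction gathers information from four arms and three post-baseline visits, so its λ is not that of one pairwise contrast: at n = 52 it is 14.6 with one arm differing, against (52/2) × 0.25 = 6.5 for a pairwise change at one visit. Nor does 9 df reach the secondary outcomes, on which Hypothesis III mainly rests; these have 3 df.

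Named contrasts do not always gain power either. A baseline-adjusted pairwise contrast at one visit has λ = n/(4(1 + ρ)). At n = 52 and ρ = 0.6 this is 8.125, giving power 0.81 unadjusted and 0.57 at α/6, against 0.76 for the interaction F when one arm differs.

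**Conclusion.** The point holds as a gap in specification. The mixed model has no named treatment contrast, its group F is not a treatment effect if baseline is among the measurements, and Hypothesis I has no named comparison with Group 4 anywhere in section 2.9.

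The power cost is moderate for the interaction F, about 10 to 35 points below a matched contrast for four-visit outcomes. For the group F it depends on the case. It loses most of its power with high correlation, with only two visits, or when the effect appears at a single visit. It does not for a sustained effect with ρ of 0.5 or less (0.83 at ρ = 0.5, n = 70).

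It would be wrong to conclude that Hypotheses I to III go untested or that neither F test bears on them. These sizes rest on d = 0.5 applied to change, equal correlation and no dropout; ρ is assumed throughout. The 9 df applies to outcomes measured on the full four-visit schedule. GAS goals are not all rated on that schedule (section 2.5.1).

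**What to change.** In section 2.9:

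1. Fit the model with one baseline mean common to all arms, or with baseline as a covariate and only post-baseline visits as responses. Do not interpret the group main effect as a treatment effect.
2. Base the model's conclusions on named 1-df contrasts, each with an estimate and confidence interval: each programme against Group 4 for Hypothesis I, ICF against each other arm for II, and NEFI against each other arm for III. These amount to six distinct pairwise contrasts. Define them by programme name, because sections 2.1 and 2.3 number NEFI and TECH in opposite order.
3. State the visit: week 3 throughout and, for Hypothesis II's primary outcomes, also 3 and 12 months. Sections 2.1 and 2.4 count follow-up from different starting points, which must be reconciled. Place GAS contrasts where each goal type is rated.
4. State a multiplicity adjustment, for example Holm, and the family of contrasts it covers.
5. Keep the interaction F as a supporting omnibus test.

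The cost is SAP wording and a few lines of R, using data already planned. The downside is some power per contrast. The 0.57 above is the Bonferroni level for six contrasts, and Holm is never worse. One family per primary outcome would hold 6 + 3 × 2 = 12 contrasts if follow-up is included, so how the families are defined matters.

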three-pronged approach to the COMprehensive Intensive REhabilitation Program after STROKE (COMIRESTROKE): **COMIRESTROKE** – **ICF**, the mostly individualized approach implementing the International Classification of Functioning, Disability and Health (ICF) model with aim to improve an individual's recovery (rather than impairment) through effective management of care (14); **COMIRESTROKE** – **TECH**, approach implementing technology-based PT" and **COMIRESTROKE** – **NEFI**, approach implementing neuroproprioceptive "facilitation and inhibition" PT.

There is very limited evidence to guide judgements regarding the rehabilitation potential following stroke (17-20). Research shows that some clinical features such as the level of consciousness, severity of hemiplegia, incontinence, dysphagia and dysphasia (21) or disease severity (22, 23) may be considered as indicators as to whether the rehabilitation process could be effective. However, confusion between predicting natural unassisted recovery and predicting responsiveness to targeted rehabilitation still remains (17). Moreover, prediction models of rehabilitation potential have never been fully and properly prospectively tested. The models considered by Prabhakaran et al., 2008 were only able to explain 47% of the variance in recovery after stroke with 53% of the variance remaining unaccounted (24). Nowadays focus shifted from the determination of rehabilitation potential to identifying clear indicators of effective rehabilitation including molecular biological readouts (25). This is reason why a wide range of patient characteristics will be collected. We consider, the patients' subjective feelings about how they have improved to be the most important aspect. Therefore, the Goal Attainment scale (GAS) together with the Patient-reported Outcomes Measurement Information System (PROMIS) Global Health, and the World Health Organization Disability Assessment Schedule (WHODAS 2.0) were chosen as primary outcomes. As secondary outcomes, measurements will be taken of motor, cognitive, psychological, speech and swallowing functions as well as functional independence.

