2.8. Hypotheses

This clinical trial will test the following scientific hypotheses:

I. COMIRESTROKE under all three settings has a positive influence on all outcomes and higher effect than control group.

II. COMIRESTROKE - ICF will have the highest impact on primary outcomes (GAS, PROMIS, WHODAS 2.0) and on such secondary outcomes that were identified as treatment goals. Furthermore, we expect the highest impact on the primary outcomes in the follow-up (three and twelve months after finishing the rehabilitation).

III. COMIRESTROKE – NEFI will have the highest effect on the secondary outcomes, mainly on motor functions. Moreover, it will most significantly lead to the initiation of plastic and adaptive processes, assessed by the level of lncRNAs in the peripheral blood.

IV. The most important predictor of effective rehabilitation will be the level of disability at admission time; however, the content of the rehabilitation will have an impact on perceived, clinical, and physiological changes of the rehabilitant.

The exploratory goals of this clinical trial are as follows:

Goal I - Improvement patterns: Considering the high number of measured outcomes, for a deeper understanding of therapy efficacy with respect to patient and treatment characteristics, this clinical trial will aim to identify groups of patients with similar improvement patterns post therapy.

Goal II - Item-level analysis: To provide a deeper understanding of the differences in effectiveness between the three therapeutic approaches, this clinical trial will plan to explore item-level between-group differences in improvement.

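### Exploratory Goal I says its patient clusters will bear on programme efficacy, but section 2.9 has no step that separates treatment effect from natural recovery and regression to the mean

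*Combined protocol and SAP*

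**What the plan says.** Section 2.8 introduces Goal I under the line "The exploratory goals of this clinical trial are as follows". Its aim is to "identify groups of patients with similar improvement patterns post therapy", and the stated purpose is "for a deeper understanding of therapy efficacy with respect to patient and treatment characteristics".

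Section 2.9 gives the method in three sentences. First, "correlations between changes in different examination scores will be evaluated using Pearson correlation coefficient and its nonparametric analogies". Then, "A cluster analysis will be performed to identify different phenotypes". Finally, "This will allow the identification of different groups of patients in relation to the efficacy of the neuro-rehabilitation programs".

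For Goal I the section does not give the variables entering the clustering, the algorithm, the number of clusters or any stability check. It names no adjustment for baseline and no comparison of clusters between arms or against Group 4.

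Section 1 itself warns that "confusion between predicting natural unassisted recovery and predicting responsiveness to targeted rehabilitation still remains".

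**The concern.** A patient's observed change is a sum: what the programme added, what would have recovered anyway, and the part that comes from an unusually good or bad baseline measurement. Clustering sees only the sum. How a given patient would have fared without the programme is not observed, so what the programme contributed can be learned only by contrasting randomised arms.

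The documents make this more than a theoretical worry:
- Section 1 reports that in most large trials both groups gained about equally.
- Hypothesis IV expects admission disability to be the leading predictor.
- Section 3 acknowledges spontaneous improvement in this phase of recovery.

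What is at stake is interpretation. A high-improvement cluster could be reported as the patients in whom rehabilitation works, and its baseline profile as an indicator of effective rehabilitation, when the analysis shows only who improved.

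**Working it through.** The plan gives no figure for the cluster analysis, so there is none to reproduce. The check has four steps.

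**1. Is there a separating step in section 2.9?**
- Hypotheses I–IV: the mixed model tests measurement, group, their interaction and covariates such as admission disability. No covariate-by-group term is named.
- Goal II: item functioning is studied by rehabilitation group, with account taken of other respondent characteristics.
- Goal I: neither arm nor baseline enters any named analysis.

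**2. Link between change and baseline.** Let Y0 and Y1 be the scores before and after, with common variance σ² and correlation ρ (both assumed). Then cov(Y1 − Y0, Y0) = σ²(ρ − 1) and var(Y1 − Y0) = 2σ²(1 − ρ), so

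corr(change, baseline) = −sqrt((1 − ρ)/2).

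- ρ = 0.5: −sqrt(0.25) = −0.50, which is 25% of change variance.
- ρ = 0.8: −sqrt(0.10) = −0.32, which is 10% of change variance.

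The equal-variance assumption matters. If the post-treatment SD is 1.25 times the baseline SD and ρ = 0.8, the covariance is proportional to 0.8 × 1.25 − 1 = 0, and the link vanishes.

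**3. What clusters of change can reflect.** This is an illustrative simulation: 210 patients (the total in section 2.6) in four equal arms, ten change scores, k-means with three clusters, 150 to 200 simulated trials per setting. The number of scores, the algorithm, the number of clusters and the variance shares are all assumptions. The effect d = 0.5 is taken from section 2.6 and applied to all three programmes against Group 4. Entries are the share of each factor's variance that lies between clusters.

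| Assumed share of change variance | d | Baseline | Natural recovery | Programme v Group 4 |
|---|---|---|---|---|
| Baseline 47% | 0 | 0.73 | 0.01 | 0.01 |
| Baseline 47% | 0.5 | 0.68 | 0.01 | 0.08 |
| Baseline 23.5%, natural recovery 23.5% | 0.5 | 0.34 | 0.34 | 0.08 |
| Baseline 10%, natural recovery 10% | 0.5 | 0.24 | 0.24 | 0.13 |
| Neither | 0.5 | 0.01 | 0.01 | 0.18 |
| Baseline 5%, natural recovery 5%, patient-specific response 50% | 0.5 | 0.09 | 0.09 | 0.12 |

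In the last row the patient-specific response itself has 0.39. The first row shows well-marked clusters with no treatment effect at all. The last two rows show that baseline and natural recovery need not dominate.

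A second simulation built the scores from baseline and follow-up values (ten tests sharing a severity factor, no arm effect, no subgroups, two clusters). Its improving cluster started 0.4 to 0.8 SD worse. For two equal clusters the between-cluster share of baseline variance is p(1 − p) × gap²: 0.25 × 0.4² = 0.04 to 0.25 × 0.8² = 0.16. The gap is real but is a small part of baseline variance.

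**4. Would baseline adjustment be enough?** In the second row, clustering on change after regression on baseline moves baseline from 0.68 to 0.00 and arm from 0.08 to 0.40. In the third row, where natural recovery is unmeasured, adjustment leaves natural recovery at 0.56 and arm at 0.12. Adjustment removes only what was measured.

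**The case against.** The best defence is that little hangs on this sentence. Goal I is labelled exploratory. Its purpose mentions treatment characteristics, so relating clusters to arm may well be intended. Programme effects are tested elsewhere in section 2.9. The wording about efficacy is loose and does not say that a cluster is the set of patients in whom treatment works. Change scores are named for the correlations, not for the clustering. Severity may also be a legitimate part of a phenotype, so removing it before clustering could discard something of interest.

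Most of this stands, and it limits the consequence. It does not rescue the inference. An exploratory label does not make clusters of change informative about efficacy, no method follows the mention of treatment characteristics, and the mixed model as described does not ask who benefits.

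Two stronger readings are tempting:
- A reader might infer that the clusters would mainly sort patients by baseline severity and natural recovery. The documents give no variance shares for this trial. The 47% in section 1 is below half, and its predictors are not listed. The correlations in step 2 leave 75% to 90% of change variance unrelated to baseline, and the simulated result reverses with the assumptions.
- A reader might infer that the plan rules out a contrast with Group 4. It is silent, which is different.

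**Conclusion.** The concern holds in a limited form. As written, section 2.9 attaches an efficacy reading to clusters that cannot carry it, because no planned step for Goal I distinguishes treatment effect from spontaneous recovery or regression to the mean. Clusters can arise, and can differ at baseline, when no programme works.

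The size of the problem in this trial is unknown. The correlations of -0.50 to -0.32 and the simulated shares are illustrations under stated assumptions, not estimates. That the clustering uses change scores is a fair inference from the aim of Goal I, not something the text states. The point does not touch the tests of Hypotheses I–IV. It bears on what the trial may say about which patients benefit, and is worth correcting before analysis.

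**What to change.** In section 2.9, for Goal I:

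1. Call the clusters descriptive recovery patterns, and state the input variables, algorithm, choice of number of clusters and stability check.
2. Replace the efficacy sentence with a comparison of cluster membership by randomised arm, including Group 4. Membership is an outcome, so its distribution can be compared between arms. Effects estimated within a cluster should not be read as randomised comparisons.
3. Add an exploratory test of baseline characteristic (for example admission disability) by arm, and base any statement about who benefits on that contrast.
4. If wanted, add clustering on baseline-adjusted change as a sensitivity analysis. It should not replace the main clustering, because unmeasured natural recovery stays in.

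No new data are needed. The costs are a more modest claim and low power for the interaction, which should be stated. For a characteristic that splits every arm in half, with the three programmes pooled against Group 4, unit SD, no dropout, two-sided α = 0.05 and power 0.80, the detectable interaction is (1.960 + 0.842) × SE:
- 210 patients in total (52.5 per arm): SE = sqrt(2 × (1/78.75 + 1/26.25)) = 0.319, giving 0.89 SD.
- 70 per arm: SE = sqrt(2 × (1/105 + 1/35)) = 0.276, giving 0.77 SD.

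Both are well above the d = 0.5 used for planning. Both cases are shown because section 2.6 gives 210 in total and 70 per group, which do not agree for four arms; that is a separate matter.
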